7.2. Study Rationale

This study is being conducted as part of the planned pharmacovigilance activities for DMF. As discussed in Section 7.1.1 and 7.1.2, the safety of DMF has been evaluated extensively in both nonclinical and clinical studies. Overall, DMF has been shown to have an acceptable safety profile. During the development of DMF, events of interest were identified, including (but not limited to) serious and opportunistic infections (based on the putative immunomodulatory mechanism of action of DMF and its potential for reducing lymphocyte counts in humans), malignancies (based on its mechanism of action, as well as results of the 2-year carcinogenicity studies in rodents), serious hepatic events (based on its potential for elevating liver transaminases), and serious renal events (based on nonclinical data identifying the kidney as a target organ of toxicity). To date, DMF has not been associated with an increased risk for these events compared with placebo. This study will further monitor for the occurrence of these types of events, and will provide data to characterize the safety profile of DMF during long-term use in routine clinical practice. This study also will provide data on populations not studied during the clinical development of DMF (e.g., patients over the age of 55 years).

CONFIDENTIAL

The information contained herein may not be used, disclosed, or published without the written consent of Biogen Idec MA Inc.

CONFIDENTIAL

The information contained herein may not be used, disclosed, or published without the written consent of
Biogen Idec MA Inc.

8. RESEARCH QUESTION AND OBJECTIVES

The purpose of this study is to better characterize the long-term benefit-risk profile of DMF in patients with MS who are prescribed DMF under routine clinical care.

8.1. Primary Objective

[figure not shown]
The primary objective of the study is to determine the incidence, type, and pattern of serious adverse events (SAEs), including but not limited to infections (including opportunistic infections), hepatic events, malignancies, and renal events, and of AEs leading to treatment discontinuation in patients with MS treated with DMF.

Note: All opportunistic infections and malignancies are considered serious and are to be reported as SAEs. Laboratory abnormalities leading to treatment discontinuation are to be reported as AEs.

8.2. Secondary Objectives

Secondary objectives of this study in this study population are as follows:

- To determine DMF prescription and utilization patterns in routine clinical practice in patients with MS.
- To assess the effectiveness of DMF on MS disease activity and disability progression in routine clinical practice as determined by the Expanded Disability Status Scale (EDSS) score and MS relapse information.
- To assess the effect of DMF on health-related quality of life, healthcare resource consumption, and work productivity.

CONFIDENTIAL

The information contained herein may not be used, disclosed, or published without the written consent of Biogen Idec MA Inc.

9. RESEARCH METHODS

[figure not shown]
9.1. Study Design

This is a prospective, global, observational study primarily designed to provide long-term safety data in patients with MS who have been prescribed DMF in a clinical practice setting as part of routine care.

DMF will not be supplied for this study. The study will collect data in an observational manner from patients aged 18 and older, who are prescribed DMF by physicians, according to the approved label in the respective country.

Enrollment of approximately 5000 patients with MS who have been newly prescribed DMF is planned. Approximately 450 sites in multiple regions, including the US, the European Union (EU), and Rest of World (ROW), will participate. Enrollment will be managed to ensure adequate representation in each region.

Safety and effectiveness evaluations will include comparisons to external databases. Health-related quality of life, healthcare resource consumption, and work productivity evaluations will be based on changes from baseline. No internal control cohort will be included in the study (see Section 9.2.2).

9.1.1. Primary Endpoint

Safety will be evaluated primarily by assessment of the incidence and incidence rate of treatment-emergent SAEs and of AEs leading to treatment discontinuation (see Section 9.7.3).

9.1.2. Secondary Endpoints

Secondary endpoints will address non-safety related study objectives, as follows:

- DMF prescription and utilization patterns will be evaluated by assessment of prescribed dosing frequency, duration of DMF use, and primary reason for discontinuation of DMF (see Section 9.7.4).
- Effectiveness of DMF on MS disease activity and disability progression will be evaluated by assessment of relapse-related endpoints (e.g., annualized

CONFIDENTIAL

The information contained herein may not be used, disclosed, or published without the written consent of Biogen Idec MA Inc.

relapse rate, time to first relapse, proportion of patients with relapse, and distribution of the number of relapses) and by assessment of EDSS-based disability progression-related endpoints (e.g., proportion of patients with progression and time to first progression), respectively (see Section 9.7.5).

- Changes in health-related quality of life measures will be evaluated over time. Healthcare resource consumption will be evaluated by assessment of endpoints such as number of hospitalizations, emergency room visits, and neurologist visits. Work productivity will be evaluated by assessment of ability to work and time needed away from work due to MS (see Section 9.7.6).

9.2. Setting

9.2.1. Prospective Cohort Study in Patients With MS

9.2.1.1. Selection Criteria

Patients aged 18 and older with MS who have been newly prescribed DMF under routine clinical care are eligible to participate in the study. Efforts will be made to recruit a variety of physicians who are representative of DMF prescribers. Eligible patients must be naïve to DMF, Fumaderm[®], and compounded fumarates at the time of enrollment, but need not be naïve to other MS treatments, and must not be currently enrolled in any other clinical trial or study except for the DMF Pregnancy Registry or other studies that, according to the study Medical Director, do not conflict with this observational study (e.g., health economic studies).

Patients with previous exposure to DMF, Fumaderm[®], and compounded fumarates are excluded so as not to introduce bias; these patients may be more or less likely to experience AEs and may fail to report AEs that occurred before study enrollment. Patients participating in other clinical studies are excluded so as not to unduly confound causality assessments when a concomitant experimental agent's safety profile has yet to be established and/or the physician is blinded to the patient's treatment assignment.

9.2.1.2. Overall Study Duration and Follow-Up

The study consists of enrollment and a follow-up period. Patient participation in the study will be for up to 5 years from enrollment. Follow-up is planned regardless of whether patients who have been prescribed DMF do not initiate treatment or discontinue treatment with DMF.

CONFIDENTIAL

The information contained herein may not be used, disclosed, or published without the written consent of Biogen Idec MA Inc.

Enrollment

The decision to enroll a patient in this study must not be made until after the Prescribing Physician and patient decide to begin DMF treatment and DMF has been prescribed. Patients agreeing to participate in the study will read and sign the consent and confidentiality statements. Enrollment data will be collected by the physician at the routine clinical visit at which DMF treatment is first prescribed (see Section 9.3.1 for details). During enrollment, the physician will also inform female patients of childbearing potential about the DMF Pregnancy Registry (in countries where the registry is conducted).

Patients enrolled in the study will be assigned unique patient ID numbers that will be used to track the patients throughout the study. Any patient identification numbers that are assigned will not be reused even if a patient does not start DMF treatment.

[figure not shown]
An individual study patient may only be included once in the study. Patients who prematurely withdraw from the study for any reason will not be eligible to re-enroll.

Follow-Up

After enrollment, the Prescribing Physician will collect patient information during routine clinical visits as described in Section 9.3.2. For the purposes of this study, routine clinical visits are defined as any visit scheduled per local standard of care. The collected information for each patient will be sent to the Contract Research Organization (CRO) managing the study (see Section 3) through their Coordinating Center (CC) approximately every 6 months for up to 5 years after enrollment. If the CC does not receive completed data from the physician on a patient for whom 6-month follow-up is expected, the CC will contact the site to remind them to complete the required data.

PROs, which include all health economic assessments, may be completed by patients during the routine clinic practice visit, or, if outside of the physician's office, within 1 week (before or after) the routine visit. Patients will receive reminders from the CC or the Prescribing Physician to complete the assessments 1 week prior to each visit, if consistent with local regulations.

All information will be sent to the CC by electronic or paper means. The information received by the CC will be stored in a secure database.

9.2.1.3. Discontinuation or Withdrawal of Patients from the Study

9.2.1.3.1. Discontinuation of DMF and Continued Participation in the Study

Patients who discontinue treatment with DMF will have the option to continue participating in the study. The Prescribing Physician will record the primary reason for

CONFIDENTIAL

The information contained herein may not be used, disclosed, or published without the written consent of
Biogen Idec MA Inc.

DMF discontinuation, including AEs (including laboratory abnormalities) leading to discontinuation. If the primary reason for discontinuation of DMF was a laboratory finding, the patient's complete history of relevant laboratory values collected during the study (starting with the most recent values prior to initiating DMF [see Section 9.3.1]) is also to be recorded. Information will be collected at routine clinical visits following the standard protocol as described in Section 9.3.2 through 30 days after the last dose. At routine visits thereafter, the standard protocol will also be followed, except SAE data collected will be limited to reports of malignancies. In the event that a patient does not have a routine visit within 6 months after his/her last dose of DMF, the physician will contact the patient by telephone to obtain the information, with the exception of laboratory data and EDSS score.

It should be noted that patients who discontinue treatment with DMF but continue to be followed in the study should have the option of restarting DMF treatment at any time within the 5-year follow-up period. Once a patient has restarted DMF, the information collected should follow the standard protocol.

9.2.1.3.2. Noninitiation of DMF and Continued Participation in the Study

Patients who are prescribed DMF but do not initiate treatment (i.e., do not take at least 1 dose of DMF) after enrollment in the study will have the option to continue participating in the study. Information will be collected at routine clinical visits following the standard protocol as described in Section 9.3.2, except for SAE and pregnancy data. Serious adverse event and pregnancy data will be collected from the first dose of DMF.

It should be noted that patients who do not initiate treatment with DMF but continue to be followed in the study should have the option of starting DMF treatment as part of routine clinical practice at any time within the 5-year follow-up period. Once a patient has started DMF, the information collected should follow the standard protocol.

9.2.1.3.3. Premature Withdrawal From the Study

Patients may withdraw consent to participate in the study at any time. If withdrawal occurs during a routine clinical visit, the Prescribing Physician will collect information one last time following the standard protocol as described in Section 9.3.2, if permitted by the patient. If a patient withdraws from the study outside of the physician's office, information will be collected one last time by telephone according to the standard protocol, with the exception of laboratory data and EDSS score, if permitted by the patient.

For patients who discontinue DMF and continue to participate in the study but subsequently withdraw, similar information will be collected one last time at the time of withdrawal, but SAE data collection will be limited as described in Section 9.2.1.3.1.

For patients who do not initiate treatment with DMF and continue to participate in the study but subsequently withdraw, similar information will be collected one last time at the time of withdrawal except SAE and pregnancy data as described in Section 9.2.1.3.2.

CONFIDENTIAL

[figure not shown]
The information contained herein may not be used, disclosed, or published without the written consent of Biogen Idec MA Inc.

9.2.1.3.4. Lost to Follow-Up

If a patient has not been in contact with the Prescribing Physician for 12 months following his or her last routine visit, the site will contact the patient by telephone to assess the patient's interest in continuing study participation. If the site is unable to make contact with the patient, a follow-up attempt must be made. A site may consider a patient lost to follow-up after 3 failed documented contact attempts, one of which must be a certified letter. If a patient's status is determined to be lost to follow-up, this must be recorded on the End of Study CRF. If the physician ascertains a patient has died, the death should be recorded and reported as described in Section 11.2.4.1.

9.2.1.3.5. Patient Transfers

In the event that a patient wishes to transfer to a different physician to receive MS care, Biogen Idec will attempt to find another study site at which the patient can continue to participate in the study. If the patient continues care with a physician who is not participating in the DMF observational study, Biogen Idec may include the new site in the observational study program, if feasible.

9.2.1.4. Study Stopping Rules

Biogen Idec may terminate this study at any time, after informing participating physicians. Physicians will be notified by Biogen Idec or designee if the study is placed on hold, completed, or closed.

9.2.2. External Control Populations

In this study, background comparator rates for events of interest (Section 8.1) and any new potential safety signals identified will be ascertained using external databases. Examples of such external databases include the following: Clinical Practice Research Datalink (CPRD), GLOBOCAN, Healthcare Cost and Utilization Project (HCUP), InVision Data Mart Multiplan (U.S. Healthcare Claims), and Surveillance, Epidemiology and End Results (SEER). The use of external databases should be a sufficient substitute for an internal control cohort for the following reasons:

- The primary objective of this observational study is to characterize the long-term safety profile of DMF; no specific hypothesis is being tested.

CONFIDENTIAL

The information contained herein may not be used, disclosed, or published without the written consent of Biogen Idec MA Inc.

- Most SAEs will be associated with hospitalization. As such, background comparator rates for SAEs calculated using health insurance claims or electronic medical record databases (e.g., CPRD) are considered to be a reasonable approximation of the background incidence rates of relevant events. For example, myocardial infarction [Austin 2002; Choma 2009; Chung 2010; Kiyota 2004; Levy 1999; Petersen 2009] and serious infection [Patkar 2009; Schneeweiss 2007] outcomes have been previously validated in claims databases.
- It is anticipated that malignancy background rates will be obtained from SEER and GLOBOCAN. These registries will provide more accurate malignancy background rates due to their large size and standardized collection and classification of cases. Malignancy background rates obtained from these registries are an appropriate comparison for an MS population since patients with MS do not appear to be at increased risk for most malignancies compared to the general population [Bahmanyar 2009; Fois 2010; Handel and Ramagopalan 2010; Koch-Henriksen 1999; Midgard 1996; Møller 1991; Nielsen 2006; Sumelahti 2004]. There have been a few studies that have suggested an increased risk of developing site-specific cancers such as breast [Nielsen 2006], brain [Bahmanyar 2009], and urinary [Bahmanyar 2009]. SEER and GLOBOCAN rates will be supplemented by MS-specific rates obtained from the peer-reviewed literature when appropriate.
- MS cohorts derived from external databases are more likely to share similar demographic and clinical characteristics with DMF-treated MS patients than would a concurrently enrolled active comparator cohort. A concurrently enrolled active comparator cohort might be subject to significant channeling biases (i.e., a form of allocation bias where drugs for the same indication are differentially prescribed based on real or perceived prognostic differences for efficacy or safety) [Petri and Urquhart 1991]. Which segment of the MS population will initiate DMF treatment and whether or not there will be any channeling bias that influences a physician's choice to prescribe DMF versus another first-line treatment cannot be predicted prior to commercial availability. Amongst the new oral MS agents, physicians may channel patients with significant cardiac or pulmonary history to an agent other than fingolimod given its cardiovascular risks and observed decreases on pulmonary function tests. If so, this may bias rates of cardiovascular and pulmonary events in fingolimod patients in comparisons to other agents. Likewise, for patients switching from another MS therapy, it is unclear where DMF will fit into the treatment algorithm. Any real or perceived differences in efficacy and safety between the available MS treatments will likely influence treatment decisions. For example, if DMF is viewed as having a strong benefit-risk profile, physicians may preferentially prescribe it to patients switching from second and third line agents such as natalizumab or mitoxantrone. This would bias the DMF cohort with patients with more aggressive disease who may be at greater risk for AEs due to the morbidity

CONFIDENTIAL

The information contained herein may not be used, disclosed, or published without the written consent of Biogen Idec MA Inc.

associated with advanced MS and its treatments. Thus, it is plausible that a concurrently recruited active comparator cohort will differ from the DMF cohort on multiple important risk factors for SAEs of interest (e.g., immunosuppressant and immunodulator use related to risk of serious infections or malignancies). Utilizing external databases will provide access to a larger pool of patients with MS and will allow flexibility in constructing comparator cohorts that reflect current MS treatment standards as they evolve over the course of the study. This will increase the likelihood of successfully using statistical techniques such as propensity score matching to calculate background rates from a comparable cohort of patients with MS who are using other first-line treatments.

- Based on the known safety profile of DMF, no special non-routine safety assessments are anticipated (e.g., annual ophthalmology examination) and thus no ascertainment bias is anticipated. The standard of care outlined in the proposed DMF prescribing information is similar to the standard of care for most other first-line MS therapies. Furthermore, the frequency of physician visits or medical procedures is not expected to differ between DMF-treated patients and similar patients with MS treated with other first-line agents. Therefore, DMF-treated patients should not be any more or less likely to receive a particular diagnosis due to recommended safety assessments.

9.3. Variables

9.3.1. Information Collected at Enrollment

Patients must be consented before any information is collected. The Prescribing Physician will collect (unless otherwise noted) and record the following information for enrollment at a routine clinical visit. See also the Schedule of Events (Section 16.1).

- demographic data
- medical history: assessment of clinically significant medical and surgical history and concomitant diseases, and known cardiovascular risk factors (e.g., smoking, alcohol consumption, patient and family history of high cholesterol, high blood pressure, cardiac disease, peripheral artery disease, arrhythmia, cerebrovascular disease, and diabetes mellitus)
- MS disease history (including type of MS, relapse history [see Section 9.3.2 for relapse definition], and the latest EDSS score based on last neurologic examination conducted prior to enrollment) and results of the latest brain MRI scan, which may include lesion count
- prior use and duration of therapies for MS (if any)
- prior use and duration of immunomodulatory, immunosuppressive (including corticosteroids), and anti-neoplastic agents (if any)
- prior use and duration of hepatotoxic and nephrotoxic agents (e.g., paracetamol, nonsteroidal anti-inflammatory drugs, antibiotics, anticonvulsants, protease inhibitors, diuretics, and lithium) (if any)

CONFIDENTIAL

The information contained herein may not be used, disclosed, or published without the written consent of Biogen Idec MA Inc.

- complete blood count (CBC) with differential, *if consistent with local regulations* ††
- other laboratory tests recommended in local label (e.g., liver and renal function tests, urinalysis) *if consistent with local regulations* ††
- concomitant use (i.e., at enrollment) of immunomodulatory, immunosuppressive (including corticosteroids), and anti-neoplastic agents, and other approved MS therapies (if any)
- concomitant use (i.e., at enrollment) of hepatotoxic and nephrotoxic agents (e.g., paracetamol, nonsteroidal anti-inflammatory drugs, antibiotics, anticonvulsants, protease inhibitors, diuretics, and lithium) (if any)
- recording of EDSS information (including Functional System Scores and Ambulation scores), based on neurological examination at enrollment, *when collected as part of routine clinical practice* (i.e., not specifically performed for the study) †††
- DMF prescription information, including prescribed dosing frequency and start date (if started on the day of enrollment; otherwise record start date at the next visit)
- patient assessment of the following outcome measures, *if consistent with local regulations*: ††††
 - physical and psychological impact of MS using the Multiple Sclerosis Impact Scale-29 Items (MSIS-29) questionnaire
 - impression of functional health and well-being using the EQ-5D-5L questionnaire and EQ Visual Analogue Scale (EQ VAS)
 - patient's assessment of the perceived effect of MS-related fatigue on daily activities using the Modified Fatigue Impact Scale (MFIS)-5 questionnaire
 - work productivity and activity impairment using the Work Productivity and Activity Impairment questionnaire: Multiple Sclerosis, Version 2.0 (WPAI-MS)
 - Healthcare resource consumption questionnaire (e.g., MS-related neurologist visits, visits to other health care professionals for MS-related and other reasons)
- pregnancy status (patient-reported, female patients)

††**Note:** In the US, physicians will be asked to record the results of the most recent CBC. If the results of a CBC conducted within 6 months of baseline are not available to be recorded, physicians will be encouraged to conduct blood draws for CBC at the time of enrollment and to record the results. To be consistent with local regulations, physicians in the EU and ROW will be asked to record the most recent CBC, liver function, renal function, and urinalysis results *if collected as part of routine clinical practice* (i.e., not specifically performed for the study). Additionally, for patients who discontinue DMF due to an abnormal laboratory test result, physicians will be asked to record all relevant

CONFIDENTIAL

The information contained herein may not be used, disclosed, or published without the written consent of Biogen Idec MA Inc.

laboratory test results collected during the course of the study *as part of routine clinical practice*.

†††**Note:** In order to assure high reliability of assessments, it is essential to have standardized examinations and consistent definitions for the EDSS. Neurostatus certification is highly recommended for all participating physicians. Physicians will be asked to provide their certification information. If they are not certified, they will be provided a copy of the interactive Neurostatus Training DVD-ROM edited by L Kappos and S Wu, Basel – Switzerland and offered a free-of-charge online certification training (www.neurostatus.net).

††††**Note:** PROs will be available to patients online or on paper to allow completion of the questionnaires outside of the physician's office. However, the questionnaires are to be completed within 1 week (before or after) the scheduled visit. Questionnaires may be completed by a proxy (e.g., family member).

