⁵ US sites will be asked to conduct blood draws for CBC (not more frequently than every 12 months unless indicated per local standard of care) and to report the results. Physicians in the European Union and Rest of World will be asked to record CBC, liver function, renal function, and urinalysis results, *if collected as part of routine clinical practice*. Additionally, in all regions, if a patient discontinues DMF due to a laboratory abnormality (see Table 7, Continued, below), physicians will be asked to record all relevant laboratory test results collected during the course of the study as part of routine clinical practice.

⁶ When collected as part of routine clinical practice.

⁷ If treatment with DMF is not started on the day of enrollment, the start date should be recorded at the next routine visit.

⁸ PROs may be assessed at a routine visit or online outside of the physician's office, *if consistent with local regulations*. If completed online, PROs should be completed within 1 week (before or after) the scheduled visit.

⁹ SAEs and pregnancy status will not be collected in patients who are enrolled in the study but do not initiate treatment with DMF. SAE and pregnancy status will be collected from the first dose of DMF.

Abbreviations: CBC = complete blood count; EDSS = Expanded Disability Status Scale; EQ VAS = EQ Visual Analogue Scale; MFIS-5 = Modified Fatigue Impact Scale-5; MRI = magnetic resonance imaging; MS = multiple sclerosis; MSIS-29 = Multiple Sclerosis Impact Scale-29 Items; PROs = patient-reported outcomes; SAE = serious adverse event; US = United States; WPAI-MS = Work Productivity and Activity Impairment questionnaire; Multiple Sclerosis.

CONFIDENTIAL

The information contained herein may not be used, disclosed, or published without the written consent of Biogen Idec MA Inc.

Table 7: DMF Study 109MS401: Study Activities (Continued)
Discontinuation of Treatment and/or Premature Study Withdrawal Visit, Chart 2 of 2

Assessments	DMF Discontinuation With Continued Study Participation		Premature Study Withdrawal Visit ¹
	First Routine Visit After Last Dose ²	Subsequent Routine Visits After Last Dose	
Date of and primary reason for discontinuation of DMF, and last prescribed dose	X		X
AEs (including laboratory abnormalities) leading to treatment discontinuation	X		
SAEs ^{3,4}	X		X ⁸
Reports of malignancies only		X ⁴	
CBC with differential ⁵	X	X	X
Other laboratory tests recommended in local label ⁵	X	X	X

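### The enrolment questionnaires may be completed up to a week after the visit at which DMF is prescribed, so an unknown share of PRO baselines can be post-dose

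*Protocol*

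**What the plan says.** The note attached to the enrolment PRO list in Section 9.3.1 says that "the questionnaires are to be completed within 1 week (before or after) the scheduled visit". Section 9.2.1.2 (Follow-Up) gives the same window for questionnaires completed away from the clinic. Footnote 8 of Table 7, Chart 1 (Section 16.1) repeats it: "If completed online, PROs should be completed within 1 week (before or after) the scheduled visit". That footnote sits on a row marked for the Enrollment (Baseline) column as well as for routine visits. None of the three exempts baseline.

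On timing, Section 9.2.1.2 states: "Enrollment data will be collected by the physician at the routine clinical visit at which DMF treatment is first prescribed". The DMF item in Section 9.3.1 asks for the "start date (if started on the day of enrollment; otherwise record start date at the next visit"), so a same-day start is expressly foreseen. Section 9.3.1 also opens with "Patients must be consented before any information is collected".

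On use, Section 9.1 says: "Health-related quality of life, healthcare resource consumption, and work productivity evaluations will be based on changes from baseline". It adds that there is no internal control cohort. Section 9.7.6 plans summaries over time and changes from baseline for each instrument.

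**The concern.** A baseline in a single-arm study has one job: to describe the patient before treatment. Here the collection rule does not guarantee that. A patient who takes the first capsule on the day of the visit and fills in the forms at home some days later has complied fully, yet the stored baseline is an on-treatment value.

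For most outcomes in this protocol there is some other reference. Section 9.1 says "Safety and effectiveness evaluations will include comparisons to external databases", but names no such comparison for quality of life, resource use or work productivity. For these, the patient's own baseline is the only reference, and they make up one of the secondary objectives (Section 8.2). A baseline already moved by treatment shifts all later changes by a fixed amount, which a larger sample does not reduce.

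An early effect is plausible for at least some instruments. Section 7.1.2 lists flushing and gastrointestinal events as the most common adverse events reported more often with DMF.

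**Working it through.** The protocol states no power, precision or effect figure for these outcomes, so there is no planned number to reproduce. The check is one of dates, followed by an illustration of size.

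**Step 1: dates.**
- Day 0 is the visit at which DMF is first prescribed and enrolment data are collected (Section 9.2.1.2).
- Earliest first dose: day 0 (Section 9.3.1, DMF prescription item).
- Questionnaire window as written: day −7 to day +7 (Sections 9.2.1.2 and 9.3.1; Table 7, Chart 1, footnote 8).
- Nothing may be collected before consent (Section 9.3.1), and the decision to enrol follows the prescription (Section 9.2.1.2). The half of the window before the visit is therefore largely unusable at enrolment, which leaves day 0 to day +7.
- Longest treatment before a compliant baseline: 7 − 0 = about 7 days.
- No section requires the questionnaire to precede the first dose. By contrast, where DMF is stopped for a laboratory finding, the laboratory history must start from values obtained before DMF (Sections 9.2.1.3.1, 9.3.2 and 11.2.1). The PROs have no such anchor.

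**Step 2: formula.** Let D be the true mean change from an untreated baseline, f the share of baselines completed after the first dose, and e the mean score shift already present in those patients. Then

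observed mean change = D − f × e.

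The documents give neither f nor e. Everything below assumes values for them.

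**Step 3: relative size.** Take e as 25% of D, in the same or the opposite direction:

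| f | Early shift in same direction as D | Early shift in opposite direction |
|---|---|---|
| 10% | 1 − 0.10 × 0.25 = 0.975 D | 1.025 D |
| 50% | 1 − 0.50 × 0.25 = 0.875 D | 1.125 D |
| 100% | 1 − 1.00 × 0.25 = 0.75 D | 1.25 D |

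The sign of the bias follows the sign of the early effect.

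**Step 4: EQ VAS points.** Suppose early tolerability problems lower the score by 2 to 5 points in 20% to 50% of patients. The mean baseline then falls by 0.2 × 2 = 0.4 to 0.5 × 5 = 2.5 points, and each later mean change is too favourable by that amount. An early rise of the same size would make it too unfavourable by the same amount.

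**Step 5: against sampling error.** In SDs of the change, the 95% half-width of a mean change is 1.96/√n. With n = 5000 (the analysis population assumed in Section 9.5) this is 0.028. An assumed shift of 0.1 SD gives a bias of 0.01 SD at f = 10%, 0.05 SD at 50% and 0.10 SD at 100%. It passes the half-width once f exceeds 0.0277/0.1, about 28%. PROs are collected only where local regulations allow, so n may be smaller. At n = 1000 the half-width is 0.062, and f would have to exceed about 62%.

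**The case against.** A reader might infer that the PRO baseline of this study is contaminated. The documents do not support that. A post-dose baseline needs three things together: forms completed outside the clinic, completed after the visit, and DMF already started. Section 9.2.1.2 allows completion at the visit itself, DMF is not supplied by the study (Section 9.1), and Section 9.3.1 provides for later starts. Many baselines may be clean. This part of the objection stands: only an unknown share can be affected.

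A reader might also infer that every later change will look better than it is. That holds only if the early effect is a worsening. The documents report no first-week PRO effect and do not say how soon flushing or gastrointestinal events appear. Nor are the instruments alike. MSIS-29 and MFIS-5 ask about the impact of MS and MS-related fatigue, and Section 9.1.2 frames time away from work as due to MS, so tolerability is a less obvious route to those scores than to EQ VAS. This stands too.

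Third, defining the analysis baseline is ordinary SAP business, and the SAP is not at hand. With the DMF start date recorded, it could set aside post-dose questionnaires, provided completion dates are captured. That is fair, and the absence of such a rule from the protocol is not the finding. But no analysis can supply a pre-dose value that the collection rule allowed to be missed.

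Finally, these are secondary outcomes, described without formal testing (Section 9.7), and Section 9.7.6 also presents plain summaries over time. This limits the weight of the point but does not remove it.

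**Conclusion.** The point holds as a weakness in a stated collection rule. The one-week window applies at enrolment, DMF may start that day, and nothing requires the questionnaire to come first. A compliant baseline can therefore follow up to about 7 days of DMF in an unknown share of patients. Because these outcomes rest on change from baseline without an internal control, any early effect of DMF on the scores carries into every later change, in either direction.

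The size cannot be determined from the documents. The figures of 0.4 to 2.5 EQ VAS points, and of 0.01 to 0.10 SD, are products of assumed shares and shifts. They show what could happen and are not evidence that it will. The primary safety endpoint is unaffected. The change is worth making because it is cheap and what is lost cannot be recovered later.

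**What to change.** Amend three places: the window in Section 9.2.1.2, the enrolment PRO note in Section 9.3.1, and footnote 8 of Table 7, Chart 1. Each should say that the enrolment questionnaires are completed after consent and before the first DMF dose is taken, and that the completion date is recorded. Questionnaires completed after the first dose count as post-baseline. The corresponding note in Section 9.3.2 stays as it is, and routine follow-up visits keep their window of one week either side. Since footnote 8 and Section 9.2.1.2 serve both enrolment and follow-up, their wording has to separate the two.

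This changes when a form is filled in. It does not touch when treatment starts, so routine care and the observational design are unaffected. With f = 0, the observed change equals D among patients who have a baseline.

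The cost is a sentence in each place, a date field and a date check. Some patients will have no usable PRO baseline, and they may differ from the rest, so their number should be reported. A missing baseline that is visible is preferable to a post-dose one that is not.
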